3.3 Intervention

Participants will receive traditional Yo-Yo training, ball-dribbled Yo-Yo training, SSGs training respectively. The intervention will last for 4-weeks, with 3 training sessions a week. These interventions will perform as regimens at the same time into the whole training. The first 2-weeks training consists of 2 sets 4-minutes exercise and a 4-minutes passive rest. During the last 2-weeks, the rest between exercise will be reduced to 3-minutes. While training, all the participants should

wear a heart rate belt (Verity Sensebi, Polar, Finland) to monitor the training intensity. Heart rate and RPE will be recorded before, during and after the training.

The Yo-Yo Intermittent Recovery 1 protocol will be implemented as a training tool. Participants should perform 4-minutes repeated 20-meter shuttle runs between two parallel lines, with running pace controlled by standardized audio cues, followed by a 10-second passive rest. The speed will initially start from 10 km/h, increasing by 0.5 km/h every stage. The termination rules will be cancelled, and participants should try to maintain maximum effort regardless of the cues.

The Ball-dribbled Yo-Yo Intermittent training requires participants performing repeated shuttle runs with a soccer ball, simulating dribbling with maximum effort in game. Each shuttle lasts 15 seconds, followed by 15 seconds of passive rest. The required shuttle distance per bout is calculated based on 110% of participant's baseline Yo-Yo IR1 terminal speed. Individualized bout distances will calculate as:

$$D = (V_t \times 110\% / 3.6) \times 15$$
 Where: D = Required shuttle distance per bout (meters), V_t = Terminal speed (km/h) from pre-test Yo-Yo IR1 (Appendix 1) and 3.6 = km/h to m/s conversion. The turning point of the shuttle run will be marked with cone for participant, where participants need to turn 180° with ball dribbled. To ensure continuity of play, two coaches will be positioned near the sidelines to provide replacement balls when necessary.

The SSGs should conduct on a 25 × 35-meter rectangular field, featuring two teams of four players each (4v4 format). Participants will be instructed to maintain maximal effort throughout the matches while prioritizing sustained ball possession. To ensure continuity of play, two coaches should be positioned near the sidelines provide replacement balls when necessary. Matches shall conduct without goalkeepers, and players are permitted unrestricted movement across the entire playing area.

The overall training plan of this study is shown in Table 1.

Table 1 *Description of 4-Week Training Program*

Weeks	Sessions	Yo-Yo IR1	Ball-dribbled Yo-Yo	SSGs
1	Baseline-Tests			
2				
		Increasing speed shuttle run	15s 110% max velocity YYIR1 ball-dribbled shuttle run	4 vs.4 Small-sided games
		10s rest	15s rest	25 ×
3	1-6	between shuttles	between shuttles	35-meter field
4		2 × 4 min bouts	2 × 4 min bouts	2 × 4 min bouts
		4min passive rest between bouts	4min passive rest between bouts	4min passive rest between bouts
5	7-12	Increasing speed shuttle run	15s 110%YYIR1 speed	4 vs.4 Small-sided games
6				

ball-dribbled					
shuttle run					
10s	rest	15s	rest		
between		between			
shuttles		shuttles			
2 × 4 min		2 × 4 min		2 × 4 min	
bouts		bouts		bouts	
3min	passive	3min	passive	3min	
rest	between	rest	between	passive	rest
bouts		bouts		between	
				bouts	

7 Post-Tests

3.4 Measurement

3.4.1 Aerobic Capacity

The aerobic ability will be assessed via Yo-Yo Intermittent Recovery 1 test. Participants should perform repeated 20-meter shuttle runs between two parallel lines, with running pace controlled by standardized audio cues, followed by a 10-second passive rest. The speed will initially start from 10 km/h, increasing by 0.5 km/h every stage. When participants fail to keep up with the set speed for the first time, they will be warned. If they fail to keep up for the second time, the test will be terminated, and completed distance shall be recorded. Participants will be requested to complete the shuttle runs before the cues sound and try to maximize the number of completed

shuttles. Heart rate (HR) and rating of perceived exertion (RPE) will be recorded before, every end of the stage, and once after the test. The participants' $\text{VO}_{2\text{max}}$ will be calculated by a regression equation: $\text{VO}_{2\text{max}} = \text{distance(m)} \times 0.0084 + 36.4 \text{ ml}\cdot\text{kg}^{-1}\cdot\text{min}^{-1}$ (Nalbant & Özer, 2018).

3.4.2 Anaerobic Capability

The anaerobic capability will be measured via three tests: Wingate Anaerobic Test (Wingate), 10-meters and 30-meters Sprint test (ST) and Repeated Sprint Ability test (RSA).

The Wingate test will conduct on a Monark 894 E ergometer (Monark, Sweden). Participant should first warm up 5-minute by cycling against a resistance of 4% body weight, followed with 2-minutes passive rest. Then, participants are required to sprint maximally for 30-seconds against 7.5% body weight resistance. Standardized strong verbal encouragement will be provided by researchers across the trials. HR and RPE will be recorded immediately pre- and post-trial, while peak power output (PPO) and mean power output (MPO) will be extracted from the sprint data.

For acceleration and maximum velocity, participants should perform 10-meter sprint and 30-meters sprint test for 3 times respectively with maximal effort on synthetic turf, 2-minute passive recovery are available between trials. Best and mean sprint times will be recorded using Witty timing System (Microgate, Italy) positioned at 0m, 10m, or 30m marks.

Sprint performance will be evaluated using three maximal trials each of 10m and 30m sprints on synthetic turf, with 2-min passive recovery between trials. Sprint times will be recorded using a custom-built infrared timing gate system (Omron E3JK-R4M1; OMRON, Japan) positioned at 0m, 10m, and 30m. Both best and mean sprint times were recorded for analysis.

Repeated sprint ability (RSA) will be evaluated through 6 × 40-meter shuttle sprints (20m + 20m with 180° turn), each shuttle separated by 20-second passive recovery. The timing gate will place at 0m and 20m position to record split times. Prior to formal testing, participants will complete a baseline 40-m maximal sprint. Trials will be postponed to 5-minutes later if the first sprint time exceeded the participants' baseline sprint time by more than 3%. The mean shuttle times, best shuttle times and decrement (decrement = mean/best) will be calculated (Michailidis et al., 2023).

3.4.3 Perceived enjoyment

Acute psychological responses will be assessed using the Affect Scale (AS), Felt Arousal Scale (FAS), Exercise Enjoyment Scale (EES), and an 8-item version of the Physical Activity Enjoyment Scale (PACES-8) following each training session (Lee et al., 2018). Scales will be provided every Saturday, immediately after the training. Before completing the questionnaires, participants received standardized instructions and were asked to reflect on their immediate feelings related to the activity just performed.

The AS is a single-item measure of affective valence during exercise, rated on a bipolar 11-point scale from -5 (very unpleasant) to +5 (very pleasant) (Hardy & Rejeski, 1989). The FAS is also a single-item measure of perceived physiological arousal, rated on a 6-point scale from 1 (low arousal) to 6 (high arousal) (Svebak & Murgatroyd, 1985). The EES assesses session-specific enjoyment using a 7-point scale ranging from 1 (not at all) to 7 (extremely) (Stanley & Cumming, 2010). These scales demonstrate established construct validity and sensitivity to exercise-related affective responses (Kilpatrick et al., 2015; Van Landuyt et al., 2000).

Overall session enjoyment was further evaluated using the PACES-8, by asking participants to rate how they feel about the physical activity they have been doing.

Items are scored on a 7-point Likert scale from 1 (unpleasurable) to 7 (pleasurable), with two items reverse-coded (Kendzierski & DeCarlo, 1991). Total scores ranged from 8 to 56, with higher scores indicating greater enjoyment. This abbreviated version has demonstrated excellent internal consistency and construct validity across populations (Mullen et al., 2011; Teques et al., 2020).

3.5 Statistical Analysis

Data analysis will be conducted using SPSS 29.0. First, descriptive statistics will be performed to summarize sample characteristics. Independent samples t-tests will be used to compare baseline differences between groups. The Shapiro-Wilk test will be applied to assess normality; if data violate normality assumptions, appropriate adjustments will be implemented.

A two-way repeated measures ANOVA (group \times time) will be utilized to examine between-group effects, time effects, and interaction effects on outcomes including aerobic and anaerobic performance. If significant interactions are detected, Bonferroni post-hoc tests will be conducted to identify simple main effects.

Effect sizes will be reported as partial eta-squared (η^2) for ANOVA results, with $\eta^2 < 0.06$ considered small, 0.06-0.14 moderate, and >0.14 large. Within-group effect sizes will be calculated using Cohen's d, where $d = 0.2$, 0.5 , and 0.8 represent small, medium, and large effects, respectively. Statistical significance is set at $\alpha = 0.05$, and results will be presented as mean \pm standard deviation (Mean \pm SD).

References

- Akdoğan, E., Yılmaz, İ., Köklü, Y., Alemdaroğlu, U., & Cerrah, A. O. (2021). The effect of isolated or combined small-sided games and speed endurance training on physical performance parameters in young soccer players. *Kinesiology*, 53(1), 78–85. <https://doi.org/10.26582/k.53.1.10>
- Badenhorst, J. (2017). *The effect of the growth spurt on strength, power, speed and agility training in boys during mid-adolescence* [PhD Thesis, North-West University (South Africa), Potchefstroom Campus]. <https://repository.nwu.ac.za/handle/10394/30657>
- Clemente, F. M., Praça, G. M., Aquino, R., Castillo, D., Raya-González, J., Rico-González, M., Afonso, J., Sarmiento, H., Silva, A. F., Silva, R., & Ramirez-Campillo, R. (2023). Effects of pitch size on soccer players' physiological, physical, technical, and tactical responses during small-sided games: A meta-analytical comparison. *Biology of Sport*, 40(1), 111–147. <https://doi.org/10.5114/biolsport.2023.110748>

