3.1 Participants

Participants should be recruited from middle school soccer teams. Participants shall fulfill all the following inclusion criteria to be included in the study: (1) be aged between 13 and 18 years; (2) have received at least one year of formal football training; (3) have no history of major sports-related injuries; (4) be in good general health, without smoking or alcohol consumption habits; and (5) have no known psychological or psychiatric disorders that may affect participation; (6) have not participated in any similar intervention within the past year; (7) attend the training sessions regularly. Participants should be excluded according to the following criteria: 1. are outside the age range of 13–18 years; 2. have less than one year of formal football training experience; 3. have a history of major sports-related injuries; 4. have chronic diseases or unhealthy habits such as smoking or alcohol consumption; 5. have known psychological or psychiatric disorders that may affect participation; 6. have participated in similar training interventions within the past year; 7. fail to attend at least 75% of the 12 training sessions.

The required sample size was calculated using G*Power 3.1 software based on a repeated-measures ANOVA (within-between interaction). The average effect size (f) was set at 0.25 (Cherni et al., 2025; Li et al., 2022), with a significance level of 0.05, and the desired statistical power of 0.80 achieved. The calculations indicated that a minimum of 42 participants are required in total, considering the 20% dropout, at least 50 participants should be recruited at the screening session.

The experimental procedures will be explained to participants and their parents at the screening-baseline. Before data collection, the written informed consent should also be provided. During the study, the participants will all attend regular schools and

football trainings. This research should receive approval from the Ethics Committee of University of Macau.

[figure not shown]

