3.2 Study Design and Procedures

This is a randomized controlled trial (RCT) that employs an experimental mixed design where group (traditional Yo-Yo, ball-dribbled Yo-Yo, SSGs) serves as a between-subject factor, while time (pre, post) functions as a within-subject factor. The participants will be randomly assigned to one of the groups: the traditional Yo-Yo group, the ball-dribbled group, SSGs group utilizing computer-based random sorting and grouping, where each participant will receive a number and will then be randomly placed into one of the four groups using Research Randomize ((Karahan, 2012; Shaw et al., 2019) When randomly grouping, the researcher in charge does not participate in the pre- and post-tests.

This research will utilize a non-blinded grouping randomization. The recruited participants who achieve the inclusion criteria will firstly be numbered in sequence then randomly allocated to one of the four groups. Secondly, all participants should experience the baseline testing within 2-weeks before the intervention. The anthropometric parameters, aerobic and anaerobic abilities will be assessed during this stage. The anthropometric indexes and one anaerobic assessment (Wingate Anaerobic Test) will be conducted in kinesiology Laboratory, University of Macau. The aerobic ability and the other anaerobic assessment (Sprint test and Repeated Sprint Ability test) will take place in the playground of a middle school. Then, the intervention will last for four weeks, with 3 training session per week, 12 sessions in total, which will take place in the playground of a middle school. Finally, the post-test stage, all the measurements conducted in the pre-test should be completed within 1-week following the last training session. During the pre- and post-test period, the researchers involved in the test were not informed of the intervention

groups of the subjects. All the procedures are shown in the flow chart as follows (figure 1).

Figure 1 *Study Flowchart*

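### The plan allows for 20% dropout, but its only model for the pre/post outcomes drops every player without a post-test; a mixed model would keep their baseline values

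*Combined protocol and SAP*

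**What the plan says.** Section 3.1 states that "a minimum of 42 participants are required in total" and then, "considering the 20% dropout, at least 50 participants should be recruited at the screening session". Raising recruitment is the only response to dropout in the document.

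Section 3.2 has two time points. After the intervention, "all the measurements conducted in the pre-test should be completed within 1-week following the last training session". Allocation is open to the players and comes before baseline testing.

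Section 3.5 gives the outcome analysis: a two-way repeated-measures ANOVA in SPSS "will be utilized to examine between-group effects, time effects, and interaction effects on outcomes including aerobic and anaerobic performance", with Bonferroni comparisons if the interaction is significant. Its only provision for adjusting the analysis concerns non-normal data. No section defines an analysis population, a rule for a missing post-test, imputation or a sensitivity analysis. Section 3.1 also lists attendance below 75% of the 12 sessions as an exclusion. That can be known only after allocation, and the text does not say whether such players are part of the 20%.

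**The concern.** Extra recruitment protects power. It does not protect the randomised comparison if the players who leave differ between arms.

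Change from baseline is correlated with baseline: on average, a player who starts low gains more than one who starts high, even with no training effect. If low-baseline players are lost from one arm and not from another, the completers' mean change in that arm shifts without any true difference between programmes. H3 and H4 in section 1.4 rest on between-arm differences in improvement, so such a shift could create or hide the patterns they predict.

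The document gives some reason to expect retention to vary by arm. The three programmes differ greatly in character, players know their allocation, and section 1.1 suggests that game-based training may appeal more to adolescents. That loss would also depend on fitness is an assumption. Deleting these players also discards baseline values that would correct for exactly this kind of loss.

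**Working it through.** **1. The plan's sample size.** Inputs from sections 3.1 and 3.2: f = 0.25, alpha 0.05, power 0.80, k = 3 groups, m = 2 times. The pre-post correlation ρ is not stated; 0.5 is assumed, with sphericity correction 1. The test is F with df1 = (k−1)(m−1) and df2 = (N−k)(m−1), and noncentrality λ = N·m·f²/(1−ρ).

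- N = 42: λ = 42 × 2 × 0.0625/0.5 = 10.5, df 2 and 39, power 0.803. The stated 42 is reproduced.
- The required N depends on ρ: 58 at 0.3 and 27 at 0.7. The stated figure is therefore consistent with ρ = 0.5.

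**2. How many players could be affected.** 20% of 50 is 10, leaving 40 pairs. The plan's own margin is 50 − 42 = 8, or 16% of 50. Ten is an upper reading, because 50 is a target at screening and the timing and make-up of the 20% are not given.

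**3. Power.** At N = 40, λ = 40 × 2 × 0.0625/0.5 = 10.0, df 2 and 37, power 0.781, against 0.803 at 42 and 0.875 at 50. The issue is bias rather than power.

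**4. Size of the bias.** Take outcome SD 1 at both times, correlation r and no true difference between arms. Then E(change | baseline) = −(1−r) × baseline, so the bias is (1−r) times the shift in the completers' baseline mean. If the lowest fraction p of an arm is lost, that shift is about φ(z_p)/(1−p). Arms of 17/17/16 are assumed.

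- 3 of 17 lost: p = 0.176, z = −0.929, shift 0.259/0.824 = 0.315 SD.
- 6 of 17 lost: p = 0.353, z = −0.377, shift 0.372/0.647 = 0.574 SD.

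Multiplying by (1−r) gives approximate biases:

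| Case | r = 0.5 | r = 0.8 | r = 0.9 |
|---|---|---|---|
| (a) 3 lowest lost in one arm, random loss elsewhere: 0.315(1−r) | 0.16 | 0.06 | 0.03 |
| (b) 3 lowest lost in one arm, 3 highest in another: 0.630(1−r) | 0.31 | 0.13 | 0.06 |
| (c) losses split 6/2/2, lowest lost in the first arm: 0.574(1−r) | 0.29 | 0.11 | 0.06 |

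Simulation with these small arms (4,000 to 5,000 trials per case) gives slightly smaller values: about 0.15, 0.30 and 0.27 SD at r = 0.5, about 0.05, 0.12 and 0.11 at r = 0.8, and 0.03 to 0.06 at r = 0.9.

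**5. Error rates under the planned testing sequence.** In the same cases the interaction test at nominal 5% rejects in about 7 to 11% of trials at r = 0.5 and 5 to 7% at r = 0.8. A given pairwise comparison, made only after a significant interaction and Bonferroni-corrected, rejects in about 3 to 6% at r = 0.5, against 1.7% under random loss.

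**6. The alternative.** A likelihood-based mixed model that uses every baseline value had bias of 0.01 SD or less in all these cases, with almost the same spread (for example 0.38 against 0.37). Under random loss neither method is biased.

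**The case against.** The strongest reply is that these cases are extreme. Each removes exactly the lowest- or highest-baseline players in an arm, and nothing in the document says that less fit players will leave a particular arm. If the tendency to leave correlates only 0.4 with baseline (assumed), the biases at r = 0.5 fall to 0.06, 0.12 and 0.11 SD. The mixed model's near-zero bias is also partly built in, because loss in the simulations depends only on baseline, which is the condition that model needs. Both points stand. They limit the size of the problem and the claim for the remedy, but they give no reason to prefer deletion.

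Some stronger readings are tempting and are not supported:

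- A reader might infer that 10 of 50 randomised players will be lost. The document gives 50 as a screening target, does not say when dropout occurs, and may count poor attenders in the 20%.
- A reader might infer that every outcome and comparison is affected. The enjoyment scales in section 3.4.3 have no pre-test, and the baseline t-tests can still use players who later leave.
- A reader might quote pairwise type I error of 11 to 13%. Those rates, for cases (c) and (b) at r = 0.5, come from an uncorrected test; section 3.5 requires a significant interaction and then Bonferroni.

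**Conclusion.** The concern holds in a limited form. The plan foresees dropout, has no rule for analysing it, and names a model that deletes the affected players and their baseline data. The resulting bias is nil if loss is random and modest if selection is mild. At the extreme it reaches about 0.30 SD at a correlation of 0.5, 0.12 SD at 0.8 and 0.06 SD at 0.9. These figures assume about 10 losses, arms of 17/17/16, normal data and loss driven by baseline differently by arm; the document gives no correlation. The change is worth making because it is cheap and costs almost no precision, not because the planned analysis is shown to fail.

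**What to change.** - **Section 3.5:** analyse the pre/post outcomes with a linear mixed model (SPSS MIXED, REML, unstructured covariance, group by time) in all randomised players with at least one measurement. Keep the interaction test and the Bonferroni pairwise comparisons. Report the completers' ANOVA as a sensitivity analysis.
- **Section 3.2:** invite players who stop training to the post-test already scheduled, and report missing post-tests by arm and reason. This helps whatever the cause of loss.
- **Section 3.1:** state that the 75% attendance criterion does not remove players from this analysis set, so that sections 3.1 and 3.5 agree.

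The cost is a few sentences, one different SPSS procedure and some follow-up effort; no extra players are needed and the training is unchanged. The model assumes data are missing at random given baseline. It does not correct loss related to response after baseline, cannot recover players lost between allocation and baseline testing, and can give slightly wider intervals.

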1.4 Hypothesis of the Study

H1: The aerobic capacity of adolescent soccer players will improve following a 4-week intervention.

H2: The anaerobic performance of adolescent soccer players will improve following a 4-week intervention.

H3: Aerobic adaptations will be equivalent between traditional Yo-Yo and ball-dribble Yo-Yo groups, with both superior to SSGs.

H4: Anaerobic performance will be equivalent between ball-dribble Yo-Yo and SSGs groups, with both superior to traditional Yo-Yo.

Chapter 2 Literature Review

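### The stated 0.80 power is for the omnibus interaction; the Bonferroni step that decides the superiority parts of H3 and H4 has about 62% per comparison and 47% for both, and three arms do not need it

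*Combined protocol and SAP*

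**What the plan says.** Section 3.1 (Participants) gives one sample-size calculation. It is "based on a repeated-measures ANOVA (within-between interaction"), with these inputs: "The average effect size (f) was set at 0.25", "with a significance level of 0.05, and the desired statistical power of 0.80 achieved". The result is a minimum of 42, raised to at least 50 recruits for 20% dropout.

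Section 3.2 defines the design: "group (traditional Yo-Yo, ball-dribbled Yo-Yo, SSGs) serves as a between-subject factor, while time (pre, post) functions as a within-subject factor". The same section also says that participants are "randomly placed into one of the four groups using Research Randomize", although only three arms are named.

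Section 1.4 states H3 as a pattern: "Aerobic adaptations will be equivalent between traditional Yo-Yo and ball-dribble Yo-Yo groups, with both superior to SSGs". H4 has the same form for anaerobic performance, with traditional Yo-Yo as the inferior arm.

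Section 3.5 plans a two-way repeated measures ANOVA and then: "If significant interactions are detected, Bonferroni post-hoc tests will be conducted to identify simple main effects". It does not say whether the pairwise contrasts are of change or of post-test values. No power is given for any pairwise comparison.

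**The concern.** A 2-df interaction test can show that the arms do not all change alike. It cannot show which arm beats which. The superiority halves of H3 and H4 each need two pairwise comparisons to succeed, and those are made only after a significant interaction and then at a Bonferroni level of 0.05/3. Error among the three pairs is therefore controlled twice.

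At stake is the chance of supporting the hypotheses when they are true. The only power figure in the plan belongs to a test that does not decide them, and the decisive step carries a penalty that a three-arm design does not need.

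**Working it through.** **Inputs.** From section 3.1: f = 0.25, alpha 0.05, N = 42. From section 3.2: k = 3 arms, m = 2 times. Assumed because the plan does not state them: equal allocation (14 per arm), pre-post correlation ρ = 0.5, sphericity, normal data with equal variances, two-sided pairwise tests with a pooled error term.

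**1. Reproduce the 42.** For the within-between interaction:
- λ = N f² m/(1 − ρ) = 42 × 0.0625 × 2/0.5 = 10.5
- df = (k − 1)(m − 1) = 2 and (N − k)(m − 1) = 39
- power = 0.803, and 42 is the smallest N reaching 0.80.

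With three arms, ρ = 0.3 would give 58 and ρ = 0.7 would give 27; four groups at ρ = 0.5 would give 48. Three arms with ρ = 0.5 is therefore the reading that returns the plan's figure.

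**2. Pairwise effect implied by the same f.** At ρ = 0.5 the variance of change is 2σ²(1 − 0.5) = σ², so the SD of change equals the SD of a single measurement. For the H3/H4 pattern (D, D, 0):
- 14 × (2/3) × D² = 10.5, so D² = 1.125 and D = 1.061 SD
- noncentrality per pair = 1.061 × √(14/2) = 2.806
- noncentral t, 39 df: power 0.621 at 0.05/3 and 0.781 at 0.05, before requiring a significant interaction.

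**3. Full procedure, by simulation: interaction test first, then pairs.**

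| 14 per arm | Each superiority comparison | Both |
|---|---|---|
| Bonferroni, change scores | 62% | 47% |
| Unadjusted, change scores | 73% | 66% |
| Bonferroni, post-test values | 55% | 42% |
| Unadjusted, post-test values | 67% | 58% |

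The post-test rows are lower although the single-test effect is the same. The interaction test works on change and the pairwise test on post-test values, and the two are only partly correlated.

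**4. Other numbers analysed (Bonferroni, change scores, both comparisons).** Recruiting 50 and losing 20% leaves 50 × 0.8 = 40, so about 13 per arm: 42%. With almost no loss, 16 per arm: 56%.

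**5. What a significant interaction would be followed by (14 per arm, Bonferroni, change scores).**
- Significant interaction without both comparisons: 0.803 − 0.468 = 0.335.
- Exactly one of the two significant: 2 × (0.620 − 0.468) = 0.304.
- Neither: 0.803 − (2 × 0.620 − 0.468) = 0.031. Counting all three pairs, no significant pair is also about 3%.

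**6. Is Bonferroni needed?** With three arms, any two true pairwise nulls imply the third. Either all three are true, and the omnibus test at 0.05 protects them; or at most one is true, and a single test at 0.05 protects it. Simulated familywise error of the unadjusted step after a significant interaction is 5.0% under the full null, and 3.8%, 4.9% and 5.0% when one arm differs by 0.5, 1.06 and 3 SD. With Bonferroni it is 4.2% under the full null and 1.7% when one arm differs greatly.

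**The case against.** Bonferroni tests after a significant ANOVA are valid and conservative, so this is a choice about power and not an error. That stands. Section 3.1 also names the interaction as the test it sizes. A reader might infer that the 0.80 is wrong, but the documents do not support that: the plan delivers 0.80 for the test it names. What is missing is the power of the comparisons that the hypotheses state.

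A reader might also infer that a significant interaction with no significant pair would be common. On change scores it occurs in only about 3% of trials. The common result, in about a third of trials, is that one of the two required comparisons fails, usually with the other significant, and that is interpretable. On the post-test reading, neither required comparison succeeds in roughly 0.803 − (2 × 0.55 − 0.42) = 0.12 of trials, which is more frequent but still a minority.

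Failing more often than not applies only to the claim that both arms are superior, and only near 42 analysed; at 16 per arm the power is 56%.

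Finally, the plan has many aerobic and anaerobic outcomes, and this change loosens its only multiplicity step. That is a fair caution. However, a Bonferroni correction over three arm pairs does not control error across outcomes either.

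**Conclusion.** The concern holds as a mismatch between the test that was powered and the tests that decide H3 and H4, together with an avoidable loss of power. Under the plan's own inputs, the Bonferroni step costs about 19 percentage points (66% − 47%) on the claim that both arms are superior, and it gives no protection that three arms need within an outcome.

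The figures rest on the predicted pattern of two equal arms and one worse arm, on ρ = 0.5, which is inferred, and on equal arms with normal data. With evenly spaced arms at the same f, Bonferroni power before requiring a significant interaction would be 77% for the extreme pair and 20% for each adjacent pair.

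It should not be inferred that dropping Bonferroni restores 80%. For both comparisons that would take about 57 analysed with unadjusted tests, or about 72 with Bonferroni. The redundancy argument needs exactly three arms. The equivalence halves of H3 and H4 are a separate matter, because no margin or equivalence test is given.

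**What to change.** First reconcile the references to four groups in section 3.2 with the three named arms; the rule below is valid only for three.

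In section 3.5, replace the Bonferroni sentence with:

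> *If the group × time interaction is significant at 0.05, the three pairwise between-group differences in change (post minus pre) are each tested at two-sided 0.05 using the pooled error term, without further adjustment (closed testing, three groups); otherwise no pairwise superiority is claimed.*

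In section 3.1, state that 0.80 is the power of the omnibus interaction, and that under the same inputs the power to show both superiority comparisons in H3 or H4 is about 66% with this rule. Also state the assumed correlation of 0.5, if that was the value used.

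The cost is a few sentences and pairwise tests on change scores without the Bonferroni option in SPSS, with no extra participants or data. Downsides: the pairwise intervals are no longer simultaneous; the chance of falsely separating the two equal arms rises from about 1.7% to 5%; and multiplicity across outcomes stays unaddressed, as it is now.
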